Study Design:	
This phase II, open label, single-center, safety and efficacy study is designed to evaluate HB-adMSCs to support immunity against Coronavirus Disease.
 
The screening period, up to 14 days long for each patient, will be used to assess eligibility. Once eligibility is confirmed, the patient will be considered enrolled.
 
Upon study completion, the investigators should know whether or not HB-adMSCs are effective to use in this population and if it does protect against the Coronavirus Disease.
 
To ensure that the drug is safe, a Medical Monitor will oversee the entire study, review any clinically significant laboratory data, including complete blood counts, serum chemistry, adverse events.

Planned Sample Size:	
Population: 55 patients.
 
The sample size required assumes a 15% drop-out of patients.

Investigational Therapy:	HB-adMSCs (Hope Biosciences adipose-derived mesenchymal stem cells) is provided as a white-yellowish solution in a 30 ml syringe. Each 20-mL contains 2×10^8 of HB-adMSCs to be diluted in a volume of 250 mL saline solution. HB-adMSCs is to be administered by IV infusion at a rate of 83 gtt/min at Weeks 0, 2, 6, 10 and 14. Each patient shall receive 5 HB-adMSCs infusions.
Treatment Duration:	The approximate maximum duration of treatment for each patient is 14 weeks (Week 0 through 14), and the approximate duration of the study is 26 weeks.
Criteria for Evaluation:	
Safety: Safety will be assessed by adverse event (AE) reporting, physical examinations, vital signs, and clinical laboratory values. Patient safety data will be closely monitored by the clinical team to ensure patient safety, as well as the Medical Monitor and DSMB.
 
Clinical Efficacy: Efficacy will be evaluated through the analysis of Complete Blood Count with differential. Exploratory measures will include changes from baseline inflammation, SF-36 and PHQ-9.

Statistical Methods and Planned Analyses:	The statistical analysis plan is defined and enumerated.

Introduction

Study Objectives and Endpoints

Study Objectives

Primary:

- To investigate the efficacy of HB-adMSCs in providing immune support against development of Coronavirus Disease by incidence of hospitalization for COVID-19, incidence of symptoms associated with COVID-19 (ie., fever, shortness of breath/difficulty breathing, and/or cough), and severity of COVID-19 associated symptoms ((fever 38C or higher, cough, shortness of breath/difficulty breathing).

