Secondary:

- To investigate the efficacy of HB-adMSCs in the prevention of upper and lower respiratory infections in a high-risk population.

Study Endpoints

Primary endpoints:

- Incidence of hospitalization for COVID-19.
- Incidence of symptoms associated with COVID-19

Secondary endpoints:

- Absence of upper/lower respiratory infections (with hospitalization criteria) up to 3 months post infusions.
- Change from baseline in leukocyte differential
- Change from baseline in C-Reactive Protein
- Change from baseline in TNF-alpha
- Change from baseline in IL-6
- Change from baseline in IL-10
- Clinically significant changes in laboratory values, vital signs, weight, and physical examination results.
- Incidence of AEs (AEs) and serious AEs (SAEs) related to the drug

Investigational Plan

This Phase II, open label, single center, assesses efficacy in a population of patients who have already banked their cells to evaluate HB-adMSCs to provide immune support against Coronavirus Disease. It is designed to be conducted over 3 periods or phases:

- **Phase 1** (Screening): Our screening process starts with a telephone call to provide a general overview of the study and discuss eligibility requirements. The study patient will receive the informed consent document by e-mail or in the pre-paid envelope provided. If, after reviewing this consent the study patient is still interested in participating in the study, he/she will need to sign and return the consent form to Hope Biosciences Stem Cell Research Foundation. This process can take up to 14 days.
- **Phase 2** (Treatments): Includes Infusion 1 (Week 0), Infusion 2 (Week 2), Infusion 3 (Week 6), Infusion 4 (Week 10) and Infusion 5 (Week 14). Subjects will be monitored at the clinical site for 1 hour following HB-adMSCs administration.
- **Phase 3** (follow-up): Includes Follow Up Week 18, 22 and End of Study at Week 26.

Safety assessments will be ongoing. A follow up phone call will be done a day after every infusion. Blood tests will include Complete Blood Count with differential, Comprehensive Metabolic Profile and Coagulation Panel screening for hepatotoxicity, cytopenia, renal failure or alterations in the coagulation cascade that might entail a safety concern for the individual. Efficacy assessments will include PHQ-9, SF-36, TNF-a, IL-6, IL-10, and CRP.

Selection and Withdrawal of Patients

Inclusion Criteria

1. Men and women 65 years of age and older (according to CDC provisions) OR

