2. Participant works in healthcare facility or other well characterized high-risk environment
OR
3. Has underlying conditions including but not limited to cardiopathies, diabetes mellitus, cancer, COPD, asthma or any other systemic autoimmune disease.
4. Subject has previously banked their cells with Hope Biosciences
5. No signs or symptoms of infection, including but not limited to, body temperature >100 F and pulse rate > 100 BPM.
6. Subject provides written informed consent prior to initiation of any study procedures.
7. Agrees to the collection of venous blood per protocol.
8. Agrees to conformational testing for SARS-CoV-2 before end of study

Exclusion Criteria:

1. Women who are pregnant or lactating, or those who are not pregnant but do not take effective contraceptive measures
2. Patients who are participating in other clinical trials or have intake of investigational drug within the previous 30 days;
3. Inability to provide informed consent or to comply with test requirements;
4. Any medical disease or condition that, in the opinion of the site PI or sub-investigator, precludes study participation. Including acute, subacute, intermittent or chronic medical disease or condition that would place the subject at an unacceptable risk of injury, render the subject unable to meet the requirements of the protocol, or may interfere with the evaluation of responses or the subject's successful completion of this trial.
5. Patients who have received a stem cell treatment within one year.
6. Receipt of any other SARS-CoV-2 or other experimental coronavirus vaccine at any time prior to or during the study.
7. Patient currently or recently symptomatic for COVID-19 or anyone with COVID-19 associated symptoms within the past 30-days

Withdrawal, Removal, and Replacement of Patients

Patients will be considered to have completed the study if they complete treatment and assessments through Week 26. A patient's investigational treatment should be discontinued if any of the following situations occurs:

- The Investigator believes that for safety reasons, it is in the best interest of the patient to stop treatment.
- The patient is non-compliant with the study visit schedule or other protocol requirements.
- The patient develops a severe allergic reaction that occurs following investigational product administration.

A patient may voluntarily withdraw or be withdrawn from the study at any time for reasons including, but not limited to, the following:

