- Patient withdrawal of consent: At any time, a patient's participation in the study may terminate at his/her request. The specific reason for patient withdrawal will be noted on the case report form (CRF).
- Lost to follow-up: The patient stops coming for visits, and study personnel is unable to contact the patient after repeated attempts (e.g., mail, or email).
- This study may be terminated at the discretion of the Sponsor or any regulatory agency.

If a patient's infusions are discontinued at any point during the trial and the patient maintains consent to contribute additional outcome information, the patient should continue to be followed through Week 26 for all safety and efficacy assessments. Investigators will be trained about the importance of retention and steps to prevent missing data.

The date and reason for withdrawal are to be documented in the CRF. The study site must immediately notify the medical monitor. The patients who withdraw prematurely must attend an early discontinuation visit if possible, at which time they will complete all assessments described in Table 2 under the Week 26 visit.

In the event that a patient discontinues prematurely from the study due to an Adverse Event (AE) or serious AE, the event will be followed until it resolves (returns to normal or baseline values) or stabilizes, or until it is judged by the Investigator to be no longer clinically significant. Once a patient is withdrawn from the study, the patient may not re-enter the study.

If the subject develops symptoms associated with COVID-19 during the conduct of this study, they will be asked to consult their personal physician and be tested for COVID-19, and to selfquarantine for at least 14 days. Quarantine must occur while waiting for COVID-19 test results. Once asymptomatic, subject may resume site visits. If the test results are positive, the subject will be asked to quarantine and may continue to receive infusions at the quarantine site. If the subject develops severe symptoms (ie., shortness of breath/difficulty breathing) they should go to the ER instead of personal physician.

Treatments

Details of the investigational product

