4. An infusion related, sustained (over 3 minutes) episode of hypoxia (SaO₂ of less than 80%).
5. Any Grade 4-5 Adverse Event as defined in the NCI CTCAE v4.0 and determined to be temporally related to the HB-adMSC infusion by the Medical Safety Monitor and/or DSMB.

After such review, resumption of dosing may be considered, including consideration for any prophylactic interventions (e.g. antihistamines or corticosteroids for injection site reactions).

Regarding SARS-CoV-2 infection, participants will be monitored for vital signs and physical examination at every visit. If the PI suspects possible COVID-19, it is at the PI's discretion to order testing. In the event the participant test results are positive for COVID-19, they will be allowed to complete treatment with quarantine site infusion visits only.

Protocol Deviations

An Investigator may not knowingly deviate from the study protocol without prior approval by Hope Biosciences and/or the IRB unless the deviations are necessary under emergency circumstances to protect the rights, safety, or well-being of human subjects or the scientific integrity of the clinical investigation. Deviations must be documented and promptly reported to Hope Biosciences and, if applicable, to the IRB providing oversight of the study.

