5.2.2. Main analytical approach

Endpoint/Variables

• Incidence of COVID-19 symptoms and Hospitalizations due to COVID-19 symptoms after Week 26 end of study
Model Specification/analysis method

• Incidence COVID-19 symptoms and Hospitalizations due to COVID-19 symptoms after Week 26 is summarized as counts and percentage

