5.4. Changes to Protocol Defined Analyses

Analysis is planned as per protocol. No deviation from the planned protocol specified analysis.

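### Neither primary endpoint is linked to a SARS-CoV-2 test result, and SAP 5.2.2 words the hospitalization endpoint differently from the protocol and from SAP 2.1 and 5.2.1

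*SAP*

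**What the plan says.** The protocol (Study Endpoints) lists two primary endpoints: "Incidence of hospitalization for COVID-19" and "Incidence of symptoms associated with COVID-19". The primary objective under Study Objectives spells out the second as "incidence of symptoms associated with COVID-19 (ie., fever, shortness of breath/difficulty breathing, and/or cough", so one symptom is enough. SAP 2.1 and SAP 5.2.1 repeat these endpoints. SAP 5.2.2, which sets out the analysis, gives the variable as "Incidence of COVID-19 symptoms and Hospitalizations due to COVID-19 symptoms after Week 26 end of study" and summarizes it by counts and percentages. SAP 5.4 states "No deviation from the planned protocol specified analysis".

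The protocol deals with testing in four places:

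- Inclusion Criteria, item 8: "Agrees to conformational testing for SARS-CoV-2 before end of study". No assay or timing is given.
- Withdrawal, Removal, and Replacement of Patients: if subjects develop symptoms, "they will be asked to consult their personal physician and be tested for COVID-19".
- Study Stopping Rules, last paragraph: "If the PI suspects possible COVID-19, it is at the PI's discretion to order testing".
- Table 2 and the laboratory list: a rapid antibody test is the only SARS-CoV-2 test, marked at Week 0 and Week 26.

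The SAP does not say that any of these results enters the primary analysis.

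**The concern.** The trial asks whether the product protects against COVID-19. Fever, cough and shortness of breath have many causes, and neither document gives a case definition, an adjudication step or a rule for an untested episode. COPD and asthma are among the conditions that can qualify a person for entry, so new cough or breathlessness from another cause over 26 weeks is foreseeable.

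The hospitalization wording adds a second problem. Read literally, SAP 5.2.2 would count an admission for symptoms without an infection being established. It would then be hard to tell a primary COVID-19 admission from an admission counted under the secondary endpoint on respiratory infections.

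All participants receive the product (SAP 2.2), so no comparator carries the same background illness. The headline percentage is the result, and its meaning depends on what was counted.

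**Working it through.** **Hospitalization wording.** Protocol Study Endpoints, SAP 2.1 and SAP 5.2.1 all attribute the admission to the disease. SAP 5.2.2 alone attributes it to symptoms. The SAP is therefore inconsistent with itself as well as with the protocol, and SAP 5.4 does not acknowledge the difference.

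**Does any rule guarantee a test for each episode?**

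- Item 8 of the inclusion criteria secures agreement to be tested at some point before the end of the study. It does not tie a test to an episode.
- The withdrawal section asks symptomatic subjects to be tested through their own physician. It does not say that the result must be recorded for the endpoint.
- The stopping-rules section lets the investigator decide.
- The scheduled antibody test can at most show infection at some time since Week 0. It cannot attribute a given cough, fever or admission.

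None of the four guarantees a recorded result per episode.

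**Is there a figure in the plan to reproduce?** No. The sample size of 55 is given with a 15% drop-out assumption, but without an event rate or precision target. Only the drop-out step can be followed: 55 × 0.85 = 46.75, or about 46 evaluable subjects.

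**Illustration of size.** The inputs are assumptions; neither is in the documents.

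- a = 26-week risk of fever, cough or shortness of breath from other causes
- c = 26-week risk of COVID-19, taking every case as symptomatic
- the two causes are taken as independent

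Proportion counted: P = 1 − (1 − a)(1 − c). Share of counted subjects without COVID-19: (P − c)/P.

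| a | c | P | Share without COVID-19 |
|---|---|---|---|
| 0.20 | 0.05 | 1 − 0.80 × 0.95 = 0.240 | 0.190/0.240 = 79% |
| 0.10 | 0.10 | 1 − 0.90 × 0.90 = 0.190 | 0.090/0.190 = 47% |
| 0.40 | 0.02 | 1 − 0.60 × 0.98 = 0.412 | 0.392/0.412 = 95% |

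The last two rows are the extremes for a from 10% to 40% and c from 2% to 10%. In the first row, with 46 evaluable subjects, 46 × 0.240 = 11.0 would be counted and 46 × 0.05 = 2.3 would have COVID-19. The reported incidence would be 24% instead of 5%. This covers the symptom endpoint only; nothing in the documents supports a similar calculation for hospitalization.

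**The case against.** Several points can fairly be made for the plan.

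- **The SAP has not replaced the endpoint.** A reader might infer that the SAP deliberately widened it. The documents do not support that: SAP 5.2.1, the section that defines the endpoints, keeps the protocol wording, and the phrase in 5.2.2 can be read as symptoms of COVID-19. What stands is inconsistent wording in the section that governs the count.
- **The testing rules need not contradict each other.** A reader might infer an outright conflict. One passage covers a subject who develops symptoms and goes to a personal physician; the other covers suspicion arising from vital signs or examination at a visit. They can be two routes. Even so, neither guarantees a test for each episode.
- **Symptom incidence is a design choice, and on it the SAP agrees with the protocol.** That is right, and is a reason not to replace the endpoint. It does not let the figure be read as COVID-19 incidence.
- **Entry criteria reduce background symptoms.** COPD and asthma belong to one of three alternative entry routes, subjects must be free of signs of infection, and those with COVID-19-associated symptoms in the past 30 days are excluded. This lowers early background rates but does not prevent new episodes over 26 weeks.
- **Diagnoses may be retrievable.** New illnesses are recorded as adverse events, hospital stays as serious ones, and events are coded in MedDRA. The CRF and programming specifications were not available to me, so a confirmed-case display there cannot be ruled out. An endpoint definition still belongs in the SAP.
- **The bias runs both ways.** With no control arm, counting non-COVID illness raises incidence, which works against the product. Counting only test-positive cases while some episodes go untested lowers it, which flatters the product. This stands, and it rules out a test-positive count as the sole headline.

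**Conclusion.** The point holds in limited form and should be corrected before analysis. As written, the symptom count admits non-COVID fever, cough or shortness of breath by definition, and the hospitalization count can admit non-COVID admissions. The testing rules and the SAP do not provide for separating them.

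The size cannot be established from the documents. The 79% figure, and the range of 47% to 95%, rest wholly on assumed risks, on independence, and on every COVID-19 case being symptomatic. They show that the definition can change the headline several-fold. A reader might infer that most counted events will be non-COVID; that is not shown. The analysis is descriptive and tests no hypothesis (SAP 3), so what is affected is the interpretation of the primary percentages.

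**What to change.** 1. In SAP 5.2.2, use the protocol wording for the hospitalization endpoint, matching SAP 2.1 and 5.2.1.
2. Keep the protocol's symptom-incidence endpoint. Report both it and hospitalization by test status: positive, negative and untested. State the assay and sampling window that make an episode test-positive.
3. Present test-confirmed COVID-19 beside the all-symptom figure. Give bounds for the untested: positive/N when untested episodes count as non-cases, and (positive + untested)/N when they count as cases. For subjects with several episodes, class as positive if any is positive, as untested if none is positive and any is untested, and otherwise as negative.
4. Record the test date and result for each episode, unless the CRF already does so.
5. Reconcile the testing statements in the withdrawal and stopping-rules sections of the protocol, and state how inclusion item 8 is met.

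The cost is SAP wording, a little more data capture and tabulation, and a protocol clarification; the protocol already asks symptomatic subjects to be tested. The drawback is that the test-confirmed figure is understated wherever episodes go untested, which is why the untested count must be shown with it.

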5.3. Secondary Endpoint(s) Analyses**5.3.1. Efficacy Endpoints / Variables**

- Change from baseline in leukocyte differential
- Change from baseline in C-Reactive Protein
- Change from baseline in TNF-alpha
- Change from baseline in IL-6
- Change from baseline in IL-10

All the secondary efficacy endpoints will be summarized descriptively using N, Mean, Standard Error of mean (SE), Standard Deviation (SD), Median and Range (Minimum and Maximum).

- Absence of upper/lower respiratory infections (with hospitalization criteria) up to 3 months post infusions

Absence of upper/lower respiratory infections summarised as counts and percentages.

5.3.2. Safety Analyses

The safety analyses will be based on the Safety analysis set, unless otherwise specified.

5.3.2.1. Adverse Events

AEs will be coded using the most recent version of the Medical Dictionary for Regulatory Activities (MedDRA).

A treatment emergent adverse event (TEAE) is defined as an event that has onset date on or after the first day of exposure to infusion treatment and on or before the last day of infusion treatment. Here the first day of exposure is defined as the first day of exposure to infusion treatment.

Treatment Adverse events (TAES) are summarised descriptively, whereas non-TEAEs are presented in listings. TAE data will be displayed in terms of the number of subjects with at least one event (N), percentage of subjects with at least one event (%) and the number of events (E).

Individual adverse events will be listed.

The details of the planned displays are in programming specification document.

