For the purposes of this study, the period of observation for collection of AEs extends from the time the patient gives informed consent through Week 26 (or early discontinuation visit). Follow-up of the AE is required until the event resolves or stabilizes at a level acceptable to the Investigator.

Intensity of Adverse Event

The intensity of the AE will be judged based on the following:

Mild	Awareness of sign(s) or symptom(s) which is/are easily tolerated
Moderate	Enough discomfort to cause interference with usual activity
Severe	Incapacitating or causing inability to work or to perform usual activities

Infusion Stopping Rules

Infusion will be stopped when:

- Allergic reaction is aroused after the product has been administered intravenously.
- Patient verbally decline the treatment at any moment prior, or during the infusion.

- Hyperpyrexia develops after infusion administration begins (core body temperature greater than or equal to 40°C) [57].
- PI may stop the study at any time, based upon PI's discretion
- Malignant Hypertension (180/120 mm/Hg)
- Sudden Severe Hypotension (30-40 mm/Hg drop from pre-infusion level)

Study Alteration Rules

If any of the following events listed below occur, administration of the study drug will be immediately suspended. The Internal Monitoring Committee (IMC), presided by the Medical Monitor will meet to review the incident and its etiology. The committee determine if it is likely related to the drug, the infusion or unrelated. If the IMC along with the Medical Monitor agree that the SAE is unlikely or unrelated to the drug, the study will be continued. If the SAE appears to be definitely drug-related, the study will be stopped. If the SAE is probably or possibly linked to the drug, the IMC will determine the risk to future patients and decide if the study should proceed or be stopped.

Study Stopping Rules

The stopping rules listed below will trigger cessation of enrollment and potential study closure pending a comprehensive DSMB safety review.

1. Any infusion related death, deemed by PI to be associated or possibly associated with study drug.
2. Three or more of the same Grade 3 or higher AEs (judged by the investigator, medical monitor or sponsor), including infusion site reactions.
3. Any event which, in the opinion of the investigator, medical monitor or sponsor, contraindicates further dosing of additional subjects.

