2.2. Study Design

Overview of Study Design and Key Features	
This phase II, open label, single-center, safety and efficacy study is designed to evaluate HB-adMSCs to support immunity against Coronavirus Disease.	
Design Features	
The trial includes,
 
 • There is a screening period of up to 14 days • A 14-week treatment period while on HB-adMSCs 
 ▪ Infusion 1 (Week 0), Infusion 2 (Week 2), Infusion 3 (Week 6), Infusion 4 (Week 10) and Infusion 5 (Week 14) • A safety Follow-up periods and end of the study or early discontinuation visit. 
 ▪ Follow up week of 18 and 22 and end of study at Week 26 • 55 Subjects
Study Intervention	
 • Intervention: HB-adMSCs (Hope Biosciences adipose derived mesenchymal stem cells) 
 ▪ Dose: 2×10^8 cells suspended in 20 ml sterile saline ▪ Route: Intravenous ▪ Regimen: Weeks 0, 2, 6, 10 and 14. ▪ 83 gts/min (250 mL/hr) • Study treatment details, 
 ▪ Each syringe contains 20 ml of cells solution with 2×10^8 cells (+20%). The syringe content is to be diluted in 250 mL of 0.9% sodium chloride.
Study Intervention Assignment	
 • All participants receive HB-adMSCs
Interim Analysis	
 • No interim analysis will be performed in this study

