7.1.5. Study Period

Adverse events will be classified according to the time of occurrence relative to the study intervention period.

Treatment emergent	Definition
Y	If event start date is not missing and is before date of first dose of study medication.
N	Any event started on or after date of first dose of study medication or event date is missing or partial

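### The SAP's treatment-emergent AE window closes on the last infusion day, leaving nominal days 100 to 183 out of the stated AE summary, and the SAP 7.1.5 flag has its labels reversed

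*SAP*

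**What the plan says.** SAP 5.3.2.1 (Adverse Events) requires a treatment-emergent AE (TEAE) to have "onset date on or after the first day of exposure to infusion treatment and on or before the last day of infusion treatment". Treatment AEs are then summarised as subjects with an event, percentage and number of events, "whereas non-TEAEs are presented in listings". The abbreviation used there for treatment AEs is not defined. I read it as TEAE, because the same sentence contrasts it with non-TEAEs. The section also promises a listing of individual AEs and leaves display details to the programming specification.

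The protocol (Adverse Events) says the AE observation period "extends from the time the patient gives informed consent through Week 26 (or early discontinuation visit". Its Table 2 schedules AE monitoring at Weeks 18, 22 and 26, and SAP 2.2 describes the time after infusion 5 as "A safety Follow-up periods and end of the study or early discontinuation visit". For a subject whose infusions are stopped but who keeps consent, the protocol's withdrawal section says "the patient should continue to be followed through Week 26 for all safety and efficacy assessments".

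SAP 7.1.5 (Study Period) gives a second rule. An event is treatment emergent = Y "If event start date is not missing and is before date of first dose of study medication", and N for "Any event started on or after date of first dose of study medication or event date is missing or partial". Nothing in the SAP says which section governs.

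**The concern.** The study has one arm, so the AE and SAE counts are its main safety result, and drug-related AEs and SAEs are a listed endpoint in SAP 2.1. A window with no lag after the last dose is hard to reconcile with the protocol's own safety procedures. The protocol calls each subject 24 hours after every infusion to ask about AEs, and tells subjects how to recognise delayed serious allergic reactions. A reaction found at the call after infusion 5, with onset that day, is one day too late for the TEAE table.

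The problem may reach subjects taken off treatment. One protocol reason for stopping is "The patient develops a severe allergic reaction that occurs following investigational product administration". If the window is applied per subject and the reaction starts the day after the infusion, the event that ended treatment is not treatment emergent.

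There is also an inconsistency between tables. SAP 5.3.1 reports respiratory infections meeting hospitalisation criteria up to three months after the infusions. Such a hospitalisation is an SAE under the protocol's definition, so the same event could count in the efficacy table and be absent from the TEAE summary.

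The reversed flag in SAP 7.1.5 is a separate risk. A programmer who follows it literally would summarise pre-dose events and no post-dose events.

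**Working it through.** The documents state no figure for the length of the window, so there is none to reproduce. The check is calendar arithmetic.

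**Inputs**
- Infusions at Weeks 0, 2, 6, 10 and 14; end of study at Week 26 (SAP 2.2).
- Study Day 1 is the day of first dose, and later days are date minus Day 1 plus 1 (SAP 7.1.6). Nominal day of week w = 7w + 1.
- Visit window ±3 days (protocol, Assessments by Week).

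**Subject given all five infusions**
- Week 14: 7 × 14 + 1 = day 99. Week 26: 7 × 26 + 1 = day 183.
- Outside the window: 183 − 99 = 84 days (days 100 to 183); 84/183 = 45.9%. Inside: 99/183 = 54.1%.
- Shortest gap with visit windows: infusion 5 on day 102, final visit on day 180: 78 days, 78/180 = 43.3%.
- Longest gap: infusion 5 on day 96, final visit on day 186: 90 days, 90/186 = 48.4%.

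**Subject who stops infusions early but is followed to Week 26, if the last day is read per subject**

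| Last infusion | Nominal day | Days outside window | Share of 183 |
|---|---|---|---|
| Week 10 | 71 | 183 − 71 = 112 | 61.2% |
| Week 6 | 43 | 183 − 43 = 140 | 76.5% |
| Week 2 | 15 | 183 − 15 = 168 | 91.8% |
| Week 0 | 1 | 183 − 1 = 182 | 99.5% |

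**The two rules side by side (five-infusion subject)**

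| Onset | 5.3.2.1 | 7.1.5 as written | 7.1.5, labels swapped |
|---|---|---|---|
| Before first dose | N | Y | N |
| Day 50 | Y | N | Y |
| Day 120 | N | N | Y |

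As written, the rules disagree on every pre-dose day and on days 1 to 99. They agree, both N, on days 100 to 183. The label error therefore does not cause the follow-up gap; 5.3.2.1 creates that gap by itself.

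Swapping the labels alone does not finish the repair. The swapped rule has no end date. It would also mark every missing or partial date Y, including a partial date whose known month or year clearly precedes dosing. AEs are collected from consent, so such dates can arise.

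**The case against.** The strongest reply is that nothing is lost. Every AE is listed, and SAP 5.3.2.1 leaves displays to the programming specification, which could add SAE, drug-related or all-AE tables without touching the TEAE definition. Vital signs and laboratory results from follow-up visits are summarised elsewhere, and the protocol's stopping rules do not use the TEAE flag. Acute infusion reactions would start on an infusion day, inside the window, and delayed reactions to every infusion but the last are inside it too. Later events may be mostly background illness.

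Most of this stands, and it limits the point. A reader might infer that late AEs go unreported or that subject protection is weakened; the documents support neither. What remains is that listings give no count or percentage, and the one AE summary the SAP does commit to excludes the follow-up period.

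Other stronger readings also go too far:
- **Early stoppers.** The SAP does not say that the last day is each subject's own, and SAP 2.2 describes a 14-week treatment period. The 112 to 182 days hold only on the per-subject reading.
- **The synopsis's 15% drop-out.** It is tempting to treat about 8 of 55 subjects as stopping infusions yet staying to Week 26. That would raise the omitted share of subject-days to (47 × 84 + 8 × 112)/10,065 = 48.1%, or to (47 × 84 + 8 × 182)/10,065 = 53.7% if they stop after infusion 1. The synopsis does not say that drop-outs stay. If they leave after infusion 4, the share is 3,948/(8,601 + 568) = 43.1%.
- **A probability that an SAE is omitted.** This needs an SAE count and a late-onset fraction, and the documents give neither.
- **Three competing AE tables.** The SAP contains two rules; the third would be a reader's own correction of 7.1.5.

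**Conclusion.** The point holds as a wrong definition, not as missing detail. SAP 5.3.2.1 keeps 84 of 183 nominal days (45.9%; 78 to 90 days with visit windows) out of its TEAE summary although the protocol collects AEs throughout. This assumes five infusions on schedule and that the undefined treatment-AE term means TEAE. The figure is a share of observation time. The share of events omitted depends on when they occur and cannot be derived from the documents. The larger figures for early stoppers are conditional on the per-subject reading.

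The reversed labels in SAP 7.1.5 are a separate, apparently clerical error, but they contradict 5.3.2.1 and need correcting. Because the data are collected and listed, this is something the sponsor should fix in the SAP and does not threaten the study itself.

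**What to change.** - **SAP 5.3.2.1:** define a TEAE as an AE with onset on or after the first infusion, up to the Week 26 visit or, for subjects who withdraw, the early discontinuation visit. Nominal coverage rises from 99 to 183 of 183 days.
- **SAP 7.1.5:** swap the Y and N labels and add the same end date. Count a missing or partial onset date as Y unless its known part shows onset before the first dose.
- **Tables, Safety analysis set:** summarise TEAEs and SAEs (subjects, percentage, events) overall and by relatedness, split by onset up to the last infusion day versus after it. The present 5.3.2.1 count then stays visible.

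The cost is two edited definitions and a few table rows. Onset date, seriousness and relatedness are already on the CRF, and infusion times are already recorded, so no visits or data are added. The downside is that AE counts will rise and take in more background illness from follow-up; the split makes that visible.
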